We will enroll menthol (n = 125) and non-menthol (n = 125) YA smokers who initiated regular smoking in the past 12-months or who initiated regular smoking more than 12 months ago, and measure appeal/reinforcement for menthol and non-menthol cigarettes and the impact of appeal/reinforcement on changes in smoking (progression, nicotine dependence, and cigarette harm perceptions) at a 6-month follow-up. Appeal/reinforcement will be assessed via two complementary measurement paradigms: one in the laboratory using a well-validated behavioral economic choice task and the other in the natural environment using ecological momentary assessment (EMA). Laboratory studies provide a great deal of efficiency and internal control, allowing for causal inference of acute subjective response; while EMA allows for similar causal sequencing of behavior, but in an ecologically valid format in the smoker's natural environment. It is hypothesized that, compared to nonmenthol smokers, menthol smokers will show greater appeal/reinforcement, both in the laboratory and via EMA, and will be more likely to show progression to regular smoking, increases in nicotine dependence, and lower cigarette harm perceptions by a 6-month follow-up. The association between menthol preference and smoking outcomes will be reduced or non-significant after including measures of appeal/reinforcement in the model; suggesting that menthol's appeal/reinforcement accounts for smoking progression. This research will isolate the unique effects of menthol in smoking and will help inform regulatory decisions about the abuse liability of menthol cigarettes and the use of flavors in other tobacco products in future studies.

Specific Aims

Aim 1 (Phase 1): Examine the absolute and relative reinforcing value (appeal) of menthol vs. non-menthol cigarettes using a validated laboratory-based behavioral economic choice task.

Aim 2 (Phase 2): Examine the subjective effects (appeal) of menthol vs. non-menthol cigarettes (own brand) during 14 days of ecological momentary assessment (EMA) in the natural environment.

Aim 3 (Phase 3): Examine the degree to which laboratory (Phase 1) and EMA (Phase 2) measurements of menthol appeal/appeal causally impact (i.e., mediate) the association between menthol brand preference at baseline and 6-month smoking outcomes (progression, increased nicotine dependence, lower cigarette harm perceptions).

Study Design

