Phase 3 will examine the degree to which laboratory and EMA measurements of menthol appeal causally impact (i.e., mediate) the association between menthol brand preference at baseline to 6-month smoking outcomes. Participants will complete a follow-up survey that will be scheduled to occur 6 months after they are enrolled in the study to assess cigarette smoking (frequency and intensity in the past 30-days), nicotine dependence, absolute smoking harm perceptions ("How harmful are cigarettes to your health?"), and relative smoking harm perceptions ("Compared to non-menthol cigarettes, how harmful to your health are menthol cigarettes?"). Follow-up assessment can be completed either in-person, or via telephone or web-assessment (if in-person follow-up is not viable). Participants will also be asked to complete two interim assessments (2-months and 4-months post enrollment) to enhance retention rates through the 6-month follow-up. These surveys will be brief and query about tobacco use behavior in the past 30-days. Participants will be given a reminder notification approximately two-weeks before their scheduled follow-up assessment (timeframe may be a few days longer or shorter due to holidays). All other baseline variables will be re-assessed at the follow-up, in addition to questions about cessation attempts and new tobacco product initiation, including flavored tobacco use (where applicable). We will use several strategies to encourage completion of the study by providing participants: 1) a calendar of their appointments throughout the study; 2) reminder calls the day prior to a scheduled visit; 3) monetary incentives at each visit; and 4) a completion bonus.

Participants

Participants will be $n = 125$ menthol and $n = 125$ non-menthol young adult (YAs) who started smoking regularly in the past 12-months or initiated regular smoking more than 12 months ago.

Participant Recruitment

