Patterns of missing data, attrition rates, distributional properties of dependent and other measures, and correlations among all measures will be assessed. We will control for potential variables related to missing data and utilize multiple imputation methods (expectation maximization algorithm). Analysis of EMA data will use hierarchical linear modeling (HLM, which provides flexibility in handling missing data such that robust estimates can be obtained even when data are missing at random (MAR). Models for Aim 2 will examine effects of cigarette type (menthol vs non-menthol) at the day-level on predictions of subjective response (satisfaction, reward, craving reduction, physical sensations like throat grab) in that same smoking episode, and subjective response at time t (e.g., morning) predicting smoking behavior (number of cigarettes, any smoking, craving) occurring at subsequent points in time to determine the impact of subjective response on continued use by menthol status (controlling for cigarette consumption and subjective response from the previous report). A sub-group of respondents may have fixed (unchanging) ratings of subjective response over the course of 14 days, although this is unlikely given our pilot study data suggesting that daily subjective response varies significantly in this age group. We will examine baseline and daily factors that set “no changers” apart from those whose show fluctuations in subjective response. These factors will be used as covariates in models. Within-person slopes capturing associations between cigarette type and subjective response will be saved and used in Aim 3 regression models to predict 6-month smoking outcomes. Covariates with $p < .05$ will be retained in final models.

Analyses will control for the order in which study phases were completed (e.g., Phase 1 vs Phase 2 first).

Phase 3/Aim 3 Analyses

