Primary Outcomes: (a) number of days smoked cigarettes in the past 30-days, (b) number of cigarettes smoked in the past 30-days, (c) nicotine dependence; and (d) continuous ratings of harm perceptions (relative and absolute). **Secondary Outcomes:** (a) number and use of non-cigarette tobacco products used in the past 30-days (or onset of use of non-cigarette tobacco product use, if none at baseline), (b) number and use of non-cigarette flavored tobacco products in the past 30-days (including assessment of type of flavor used, like candy, fruit, alcohol, etc); and (c) intentions to use menthol cigarettes (among non-menthol smokers).

Intentions to use menthol cigarettes will also be assessed at follow-up among those reporting non-menthol as their preferred brand at baseline, using a modified 3-item algorithm: (1) “Do you think that you will try a menthol cigarette in the next 6-months? (2) “Do you think you will use a menthol cigarette anytime during the next month?” [we will assess next month and 6-months to increase variability]; (3) “If one of your best friends offered you a menthol cigarette, would you use it?” (“definitely yes,” to “definitely not”). Because of a range of possible responses, intentions may change among some

participants, making it a reasonable outcome measure. It is possible that some YAs may stop smoking over the course of the 6-months. We will examine baseline, laboratory, and EMA findings that set these individuals apart from those who continue to smoke, as such information could be useful to FDA.

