The main outcome analyses for Aim 3 will examine the predictive validity of laboratory (Phase 1) and EMA (Phase 2) outcomes on changes in the 6-month outcomes of interest, and the degree to which laboratory and EMA ratings of appeal/reinforcement account for (i.e., mediate) the association between menthol brand preference at baseline and smoking behavior change. Hierarchical regression models (continuous or binary logistic) will predict the 6-month outcome of interest, controlling for baseline levels of the outcome in interest and relevant demographics (gender, race/ethnicity, age of smoking onset) in Step 1, baseline menthol status in Step 2, and then laboratory or EMA-derived slopes Step 3. Models will be conducted separately using Phase 1 and Phase 2 measurements of appeal/reinforcement. Mediation will be reflected by a reduction in the association between baseline menthol preference and smoking outcomes after including the requisite measure of appeal/reinforcement in the model. Covariates with $p < .05$ will be retained in final models.

Exploratory analyses will examine changes over time in tobacco use behavior from baseline, 2,4, and 6-months. All data collected during the course of the study, survey and bio-specimen results, will be maintained for future use in cross-reference against new and continued data collection.

Human Subjects Protection

Potential Risks

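### The main Aim 3 models leave out the 2- and 4-month smoking data, and the plan does not say whether missing 6-month values are imputed or from what

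*Combined protocol and SAP*

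**What the plan says.** **Design.** Under Study Objective: "We will enroll menthol (n = 125) and non-menthol (n = 125) YA smokers". Phase 3 Overview and Experimental Design adds "two interim assessments (2-months and 4-months post enrollment) to enhance retention rates through the 6-month follow-up", and describes their content: "These surveys will be brief and query about tobacco use behavior in the past 30-days". Under Compensation, each is paid at $15.

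**Outcomes.** Phase 3/Aim 3 Analyses lists the primary outcomes as "a) number of days smoked cigarettes in the past 30-days, (b) number of cigarettes smoked in the past 30-days, (c) nicotine dependence", followed by (d) relative and absolute harm perceptions. Outcomes (a) and (b) use the same 30-day window as the interim surveys.

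**Main model.** "Hierarchical regression models (continuous or binary logistic) will predict the 6-month outcome of interest, controlling for baseline levels of the outcome in interest", with demographics in Step 1, menthol status in Step 2 and the laboratory or EMA measure of appeal in Step 3. Mediation is read from the fall in the menthol coefficient between Steps 2 and 3.

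**Interim data.** The only analysis that names them is this: "Exploratory analyses will examine changes over time in tobacco use behavior from baseline, 2,4, and 6-months".

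**Missing data.** The Aim 3 section states no method. Under Phase 2/Aim 2 Analyses the plan says "We will control for potential variables related to missing data and utilize multiple imputation methods (expectation maximization algorithm", and then turns to the EMA phase: "Analysis of EMA data will use hierarchical linear modeling".

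**The concern.** A participant who answers the month-4 survey and misses month 6 has given a recent report of the behaviour that outcomes (a) and (b) measure. The main models have no place for that report. If the 6-month value is not imputed, the person leaves the regression. If it is imputed without the interim values, the best available predictor is ignored.

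The sponsor plainly expects some attrition: the interim surveys and the completion bonus are there to limit it. The plan also foresees that some participants may stop smoking during the six months. If people whose smoking has changed by month 4 are more or less likely to return, those who answer at month 6 are a selected group, and baseline covariates do not fully account for the selection. At stake are some bias and lost precision in the menthol association with the two smoking-quantity outcomes.

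**Working it through.** **1. Is there a plan figure to reproduce?** No. The documents give 125 per group but no power calculation, effect size, SD or expected dropout. The rates and correlations below are all assumptions.

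**2. When is the 6-month-only regression biased?** Take a standardised outcome with baseline Y0 and menthol indicator M:

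- Y4 = 0.6·Y0 + 0.4·M + 0.8·e4
- Y6 = 0.6·Y0 + 0.4·M + 0.8·e6, with corr(e4, e6) = ρ

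The within-group variance is 0.36 + 0.64 = 1. If loss depends only on Y0 and M, completers still satisfy the Y6 equation and the regression is unbiased. If loss depends on Y4, it depends on e4. Because ρ > 0, e6 no longer has mean zero among completers given Y0 and M, and the menthol coefficient shifts. Conditioning on Y4 removes the shift.

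**3. Size of the bias.** Settings: n = 250, true menthol effect 0.4, ρ = 0.6 or 0.8, 13-26% lost at month 6, logistic loss in Y4 with the same odds ratio (OR) in both groups, month-4 data for everyone, 4,000 data sets per setting.

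| Loss mechanism | Bias, 6-month only | Bias, Y4 used | Variance ratio (6-month only / Y4 used) |
|---|---|---|---|
| OR 1 | about 0 | about 0 | 1.05 to 1.14 |
| OR 2-3 | -1.8% to -7.5% | within about 1% of zero | within 1.03 to 1.15 |

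In absolute terms the bias is 0.4 × 0.018 = 0.007 to 0.4 × 0.075 = 0.030. The estimator's SD is about 0.11, so this is 0.007/0.11 = 0.06 to 0.030/0.11 = 0.27 of a standard error. The variance ratios are before imputation noise. On the standard-error scale they are √1.03 = 1.015 to √1.15 = 1.072, an excess of about 1.5% to 7%.

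**4. Closed-form check of the variance ratio under random loss.** With fraction p lost and Y4 known for all, the ratio is 1/(1 − pρ²).

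- p = 0.13, ρ = 0.6: 1/(1 − 0.13 × 0.36) = 1/0.9532 = 1.05
- p = 0.20, ρ = 0.8: 1/(1 − 0.20 × 0.64) = 1/0.872 = 1.15
- p = 0.26, ρ = 0.8: 1/(1 − 0.26 × 0.64) = 1/0.8336 = 1.20

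The simulated range is of the right order, but 15% is not a strict ceiling.

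**5. Precision when not everyone lost has month-4 data.** Here the information about month 6 is summed over dropout patterns (likelihood analysis of baseline-adjusted 2-, 4- and 6-month values, missing at random). Assumed correlations are 0.5 to 0.8, either constant or decaying with time. Losses are either spread evenly over the three intervals or all after the month-2 survey.

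| Loss before month 6 | 6-month-only n per group | Effective n per group using interim values |
|---|---|---|
| 10% | 125 × 0.9 = 112.5 | about 114 to 117 |
| 20% | 125 × 0.8 = 100 | about 102 to 108 |
| 30% | 125 × 0.7 = 87.5 | about 90 to 99 |

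At 20% loss, the difference detectable with 80% power at two-sided 0.05 improves by only 0.003 to 0.013 SD.

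**The case against.** **The imputation may already reach Aim 3.** The paragraph holding the imputation sentence opens broadly, with attrition rates and correlations among all measures. The same section also carries a general rule on the order of phases. A reader might infer from the Aim 3 section's silence that a complete-case analysis is planned. The documents do not support that: the reach of the imputation is unstated. What stands is that nothing extends it to the 6-month outcomes or names the interim values as inputs.

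**The interim data are used.** A reader might infer that someone lost after month 2 or 4 contributes nothing to the smoking outcomes. The exploratory analyses over 0, 2, 4 and 6 months contradict that. The gap is confined to the main models.

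**Two primary outcomes are outside the point.** The interim surveys are described as brief and about tobacco use. Nicotine dependence and harm perceptions are not listed in them. The plan also does not say that days and cigarette counts are asked in the same form as at month 6.

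**The effect is small and conditional.** No dropout data support the assumed link between loss and month-4 smoking. A repeat with other loss intercepts gave biases of 0.004 to 0.038 on 0.4, at most about a third of a standard error, with interval coverage still 94-95%. The simulation gives everyone month-4 data and has no mediator, so it speaks to the total menthol effect and not to the change in the coefficient at Step 3. All of this stands, and it limits the size claimed.

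**A repeated-measures model is a poor substitute here.** Under Study Design, participants enrolled during COVID-19 restrictions may wait an unspecified time for the laboratory sessions. Their laboratory mediators could post-date the month-2 or month-4 outcome. This objection stands against that remedy, but not against using interim values as imputation auxiliaries.

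**Conclusion.** The point holds as a specific and inexpensive improvement to the main analysis of outcomes (a) and (b). It does not show that the planned analysis is invalid. Under the stated assumptions (13-26% lost, odds ratio 2-3 per unit of month-4 smoking, same mechanism in both groups, month-4 data for all), a 6-month-only analysis pulls the menthol effect toward zero by about 2-8% and has a variance about 3-15% larger. If loss depends only on covariates already in the model, there is no bias and only the precision gain remains.

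A reader might infer a much larger distortion. If loss depended on month-4 smoking in the menthol group only (OR 2-3, 21-24% lost), the same model gives a bias of -15% to -35%. Nothing in the documents suggests that pattern, so it shows what is possible and is not an estimate for this study.

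**What to change.** State a missing-data method in the Aim 3 section. For outcomes (a) and (b):

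- Keep the 6-month value as the endpoint, and keep the planned hierarchical and mediation regressions.
- Multiply impute missing 6-month values. The imputation model should contain the 2- and 4-month values as auxiliary variables, with the baseline value, menthol status, the model covariates and the laboratory or EMA measures of appeal/reinforcement. Including the appeal measures keeps the imputation compatible with Step 3.
- Report the 6-month-only analysis as a sensitivity analysis.
- Confirm how the interim items record days and cigarettes, and choose an imputation method suited to a count bounded at 30 and to a cigarette total.

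For dependence and harm perceptions, say separately how missing 6-month values are handled, since the interim surveys are not described as measuring them.

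The cost is plan wording and some programming, with no new data or participants. The limits are reliance on missing-at-random given the interim data, and no help for participants lost before month 2.

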Primary Outcomes: **(a)** the absolute reinforcing value (ARV) of menthol cigarettes from Visit 1, **(b)** the relative reinforcing value (RRV) of menthol cigarettes from Visit/Session 3 based on Choice Task responding; **(c)** RRV of own vs experimental brand based on price elasticity. ARV of menthol cigarettes will be operationalized as between subject differences in subjective ratings of menthol vs non-menthol cigarettes (satisfaction, reward, craving reduction, physical sensations) during the ad libitum smoking Visit. RRV will be measured by evaluating motivation to “work harder” for menthol versus non-menthol cigarette puffs or for one’s own brand from Visit 3. This is operationalized by the highest trial (breakpoint) that a participant successfully works for a menthol vs nonmenthol cigarette puff (or for their own vs experimental brand). Higher values reflect greater RRV of menthol cigarettes relative to non-menthol cigarettes (or their own brand vs the experimental brand. RRV of own vs experimental brand will be operationalized as cross-price elasticity of demand which measures the responsiveness of the quantity of experimental cigarettes that are self-reported to changing prices of the preferred cigarette brand.

Secondary Outcomes: **(a)** Total number of responses for the menthol versus the non-menthol-cigarette on the choice task **(b)** CO boost; and **(c)** puff topography (number of menthol versus non-menthol cigarette puffs consumed, number of minutes smoked, interval between puffs). Exploratory analyses will compare ARV and RRV.

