A 2 (menthol preference) X 2 cigarette type (usual brand versus experimental brand) mixed ANOVA will be conducted to examine main effects and interactions on the outcomes of interest. Models will examine cigarettes per day (CPD), nicotine dependence, race/ethnicity, gender, and age of smoking onset as potential covariates. Factors related to Phase 1 drop-out will be examined as potential covariates. If nicotine and CPD are collinear, the most significant predictor of the outcome will be retained in the model. Significant interactions will be followed up with individual contrasts of cell means using Fisher’s Least Significant Difference tests. In exploratory analyses, a 2 (menthol preference) X 4 (race/ethnicity: White, Black, Other, Hispanic) between-subjects ANOVA and a 2 (menthol preference) x 2 (gender) between subject ANOVA will be conducted separately for the BL Visit to evaluate differential reactions to own brand cigarette smoking by race/ethnicity and by gender. Comparison of own brand/usual brand and experimental cigarette ratings will also be made to determine the perceived similarity of the experimental cigarette to one’s own brand and as a function of gender and race/ethnicity. NOTE: We expect that ratings of appeal/reinforcement for the experimental cigarettes will be lower than ratings of appeal for usual brand. Ratings of experimental cigarettes will be examined as a potential covariate in Aim 3 models. Age of smoking initiation will also be examined as a potential covariate. Covariates with $p < .05$ will be retained in final models.

Phase 2/Aim 2 Analyses

Primary Outcomes: (a) within-day subjective response (craving reduction, satisfaction, psychological reward, physical sensations like throat grab) to the most recent cigarette smoked (menthol vs non-menthol); (b) betweenday subjective response.

Secondary Outcomes: (a) Aggregate ratings of subjective response (over the course of 14 days) by baseline menthol brand preference (at the person-level, rather than by day); (b) changes over the course of days (creating an average change score for each person); (c) within-person variability by calculating the standard deviation of daily cigarette reward, satisfaction, craving reduction, and throat hit ratings for each person; (d) cigarettes per day (within-day, over days); and (e) craving intensity (within-day, over days).

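### Aim 3 reads any shrinkage of the menthol coefficient as mediation, with no interval or test; in linear models it shrinks in about half of trials when appeal mediates nothing

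*Combined protocol and SAP*

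**What the plan says.** Under Data Analysis Plan, Phase 3/Aim 3 Analyses, hierarchical regressions (linear or binary logistic) predict each 6-month outcome. Step 1 holds the baseline level of the outcome and demographics, Step 2 adds baseline menthol status, and Step 3 adds the laboratory or EMA measure of appeal. The criterion is then: "Mediation will be reflected by a reduction in the association between baseline menthol preference and smoking outcomes after including the requisite measure of appeal/reinforcement". The only significance threshold in that section concerns which covariates to retain. The Study Objective section is no stricter: it accepts either a smaller association or a loss of significance.

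The two component paths do appear in the plan, in separate places:

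- **Appeal to outcome.** The main Aim 3 analyses are also to "examine the predictive validity of laboratory (Phase 1) and EMA (Phase 2) outcomes on changes in the 6-month outcomes of interest".
- **Menthol to appeal, laboratory.** Aim 1 defines absolute reinforcing value as "between subject differences in subjective ratings of menthol vs non-menthol cigarettes".
- **Menthol to appeal, EMA.** An Aim 2 secondary outcome is "Aggregate ratings of subjective response (over the course of 14 days) by baseline menthol brand preference". What enters Step 3, however, is a different quantity: "Within-person slopes capturing associations between cigarette type and subjective response will be saved and used in Aim 3 regression models". No comparison of those slopes by baseline menthol preference is stated.

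The mediation conclusion is not made conditional on any of these results.

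**The concern.** A coefficient almost always moves when a variable is added to a regression, and it must move one way or the other. A rule that counts any movement toward zero as evidence therefore needs a yardstick for chance, and none is given.

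Aim 3 is one of three aims. It is worded causally and is meant to inform regulation of menthol. The number of looks makes matters worse. There are five primary outcomes: days smoked, cigarettes smoked, dependence, and relative and absolute harm perception. The plan adds: "Models will be conducted separately using Phase 1 and Phase 2 measurements of appeal/reinforcement". That gives at least 5 × 2 = 10 mediator–outcome pairs, and more if several appeal measures per phase are used.

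**Working it through.** **Inputs.** The design has 125 menthol and 125 non-menthol smokers (Study Objective). The documents give no effect size, SD, dropout rate or error rate for Aim 3, so there is no figure to reproduce and every effect size below is an assumption, in SD units. Notation: *a* is menthol → appeal; *b* is appeal → outcome given menthol; *c* is the menthol coefficient at Step 2; *c′* is the menthol coefficient at Step 3.

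**Step 1: the identity.** For least squares on the same rows with the same covariates,

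ĉ − ĉ′ = â × b̂.

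In simulation with the baseline outcome and one further covariate in every step, the two sides agreed to about 1e-15.

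**Step 2: the sign under no mediation.** If *b* = 0, b̂ is symmetric about zero; if *a* = 0, â is. Either way P(â × b̂ > 0) is about 0.5. When menthol has a real association with the outcome, a reduction occurs essentially whenever the product has the sign of ĉ, so the probability is about one half. A larger sample shrinks the size of the movement but leaves its sign a coin flip.

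**Step 3: simulation.** A reduction means that the absolute menthol coefficient is smaller at Step 3 than at Step 2. There were 20,000 runs per setting (6,000 at n = 1,000, 8,000 for the covariate-adjusted row). No-mediation settings were *b* = 0 with *a* = 0, 0.2, 0.5, 1.0, and *a* = 0 with *b* = 0.2, 0.3, 0.5.

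| Setting, no mediation | Trials showing a reduction |
|---|---|
| Menthol effect 0.355; n = 150, 200, 250, 1,000 (28 settings) | 49–51% |
| Same effect, n = 250, with covariates | 49–50% |
| Menthol effect 0.2, n = 250 | 48–53% |
| No menthol effect, n = 250 | 42–58% |

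A separate simulation, adjusted for the baseline outcome, gave 49–52% at 125 per group when the menthol effect was 0.2 or 0.4. The alternative criterion in the Study Objective is not calibrated either: among trials with a significant Step 2 menthol effect, significance was lost at Step 3 in 0.5–43% of no-mediation trials, depending on the setting.

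**Step 4: does reading one path alongside rescue the rule?** n = 250, menthol effect 0.355:

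| Extra requirement at p < .05 | False reductions, *b* = 0 | False reductions, *a* = 0 and *b* > 0 |
|---|---|---|
| Appeal predicts outcome | 2.5–2.7% | 44%, 50%, 50% (*b* = 0.2, 0.3, 0.5) |
| Menthol groups differ in appeal | 17%, 49%, 50% (*a* = 0.2, 0.5, 1.0) | 2.5–2.7% |

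Requiring both gives 0.1–2.7% over all settings. Only the combination works, and the plan does not state it.

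**Step 5: ten pairs.** Expected false reductions are 10 × 0.5 = 5. With outcome/mediator correlations of 0.3/0.3, 0.5/0.5 and 0.7/0.5 (3,000 runs per setting), the simulated mean is 4.9–5.1.

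| Ten pairs, n = 250 | At least one false reduction | Also requiring appeal to predict outcome |
|---|---|---|
| *b* = 0 (*a* = 0.5, 1.0) | 89–98% | 12–19% (mean 0.23–0.25) |
| *a* = 0, *b* = 0.3 | 67–70% | 67–70% (mean 4.9–5.1) |

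**Step 6: the alternative.** A 95% percentile bootstrap interval for *a* × *b* at n = 250 (1,500 runs of 1,000 resamples) gave false claims in 0.1–5.9% of trials per pair.

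**The case against.** The strongest reply is that the section describes how far appeal accounts for the association, which is the language of estimation, and that the hypothesis is a chain: menthol smokers show greater appeal, they progress more, and the association then weakens. Investigators who read all three links together would make few false claims. On the figures above, requiring both paths gives 0.1–2.7%.

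It can also be said that *a* = 0 is implausible for the Visit 3 breakpoint, because participants are selected for smoking one type at least 80% of the time. Once *a* is clearly nonzero, a false reduction needs *b* = 0, and the predictive-validity result would catch most of those.

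The point about the breakpoint stands for that measure, so applying *a* = 0 to all ten pairs is a worst case. It does not cover own-brand ratings or the EMA slopes. Nor does the chain repair the criterion: the hypothesis describes it, but the analysis section does not require it, and an analyst who follows the written rule may report mediation from a reduction alone.

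Other limits also stand. The one-half figure is for linear models; logistic coefficients can shift without mediation when a predictor is added, and that case was not simulated. The primary outcomes all suit linear models. An interval for the indirect effect deals with chance, not with confounding between appeal and outcome. The bootstrap figures use no covariates and do not model the estimation error in saved EMA slopes.

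**Conclusion.** The criterion is wrong as written and should be changed before the Aim 3 analysis. With a real menthol association and no mediation, the linear-model coefficient shrinks in about 50% of trials (42–58% if menthol has no effect at all), and about 5 of 10 primary pairs would be expected to show a reduction. The effect sizes are assumed, but the one-half result follows from symmetry and hardly depends on them. The family-level figures depend on the assumed correlations and on which path is zero.

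**What to change.** Replace the criterion sentence with text such as:

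> For each mediator–outcome pair the indirect effect (menthol → appeal multiplied by appeal → 6-month outcome) will be estimated with a 95% bootstrap interval. Both models will include the baseline outcome, phase order and the same covariates and will be fitted to the same participants; the outcome model will also include menthol status. Mediation will be claimed only if the interval excludes zero. Intervals are not adjusted for multiplicity, and the number of mediator–outcome pairs examined will be reported.

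Phase order is included because the Aim 2 section already says: "Analyses will control for the order in which study phases were completed". Any binary outcome needs its effect scale named, and the plan should say how the bootstrap combines with the planned multiple imputation.

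The cost is a short change to the text, slightly more programming and no new data. The downside is fewer mediation claims. Power for assumed indirect effects (Monte Carlo error up to about 1.3 points):

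| Interval and assumed effect | n = 250 | n = 200 | n = 150 |
|---|---|---|---|
| 95%, 0.5 × 0.2 SD | 86% | 74% | 55% |
| 95%, 0.5 × 0.3 SD | 97% | 93% | 80% |
| 99.5%, 0.5 × 0.2 SD | 56% | 40% | 22% |

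Unadjusted over ten pairs, a joint test of both paths at .05 still gives at least one false claim in about 25–38% of trials (*b* = 0) or 9–10% (*a* = 0, *b* = 0.3). That is why the number of pairs must be reported. A 99.5% interval (1 − 0.05/10) is an optional guard at the power shown in the last row.
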